12.2.14. Delay Discounting

In this experiment you will be presented with two amounts of money to choose between. One of the amounts will be available now and the other will be available in the future. Your job is to indicate which option you would prefer by pressing "q" for the left option and "p" for the right option.

You should indicate your true preference because at the end of the experiment a random trial will be chosen and you will receive a bonus payment proportional to the option you selected at the time point you chose.

\$54 today	\$55 in 117 days
\$55 today	\$75 in 61 days
\$19 today	\$25 in 53 days
\$31 today	\$85 in 7 days
\$14 today	\$25 in 19 days
\$47 today	\$50 in 160 days
\$15 today	\$35 in 13 days
\$25 today	\$60 in 14 days
\$78 today	\$80 in 192 days
\$40 today	\$55 in 62 days
\$11 today	\$30 in 7 days
\$67 today	\$75 in 119 days
\$34 today	\$35 in 186 days
\$27 today	\$50 in 21 days
\$69 today	\$85 in 91 days
\$49 today	\$60 in 89 days
\$80 today	\$85 in 157 days
\$24 today	\$35 in 29 days
\$33 today	\$80 in 14 days
\$28 today	\$30 in 179 days
\$34 today	\$50 in 30 days
\$25 today	\$30 in 80 days
\$41 today	\$75 in 20 days
\$54 today	\$60 in 111 days
\$54 today	\$80 in 30 days
\$22 today	\$25 in 136 days
\$20 today	\$55 in 7 days

12.2.15. Opioid Purchase Task

Instructions	
The following questionnaire will ask you how many of your chosen opioids you would purchase depending upon how much they cost. Imagine that you will have to consume all purchases in a single day, you cannot stockpile or get the opioids from another source, and you have no opioids available from previous days.	
How many opioid pills would you purchase if they were:	Number they would purchase:
Free?	
\$0.25	
\$0.50	
\$1	
\$1.50	
\$2	
\$2.50	
\$3	
\$4	
\$5	
\$6	
\$7	
\$8	
\$9	
\$10	
\$15	
\$20	

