3.5. Sample Size and Population

Approximately 40 participants will be recruited from UTHSC's Center for Addiction Science (CAS) for this study. We will randomize 20 participants to the CM group, and 20 participants to the BSM group.

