7. ELIGIBILITY CRITERIA

Participants must meet the following eligibility criteria to participate in this study:

- Present for an appointment at CAS or ARC for buprenorphine-naloxone treatment of OUD
- Be eligible for buprenorphine-naloxone treatment (e.g., Suboxone, Bunavail, Zubsolv) as determined by [name]
- At least 18 years of age or older
- Access to a telephone
- Ability to understand consent procedures
- Physician confirmation of a "regular" initiation visit schedule (to ensure completion within pilot study window)

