12.2.13. Timeline followback

Today's date:							
	(fill in day of the week)						
	(example) Monday	(example) Tuesday	(example) Wednesday	(example) Thursday	(example) Friday	(example) Saturday	(example) Sunday
Did you have any illicit substances or	Yes / No						

alcohol on   day?							
If yes to alcohol: Number of standard drinks on this day?	# drinks						
Marijuana on this day?	Yes / No						
Cocaine on this day?	Yes / No						
Crack on this day?	Yes / No						
Amphetamine or other stimulant on this day?	Yes / No						
Opioid drugs that weren't prescribed to you? (not including fentanyl or methadone)	Yes / No						
Heroin on this day?	Yes / No						
Hallucinogens, including MDMA/ecstasy on this day?	Yes / No						
Sedatives and hypnotics, excluding Benzodiazepines on this day?	Yes / No						
Benzodiazepines on this day?	Yes / No						
Inhalants on this day?	Yes / No						
Fentanyl on this day?	Yes / No						
Methadone on this day?	Yes / No						

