Statistical Analysis Plan: SMART Project 3 (Efficacy Study)

Because these analyses will focus on determining and intervention feasibility and satisfaction, and preliminary intervention effect sizes (with less concern focused on testing for statistical significance), outcome analyses will be conducted using a separate analysis for each outcome at each follow up observation. To compare groups, baseline and follow up variables will be entered into a 5 (baseline vs. follow ups at 1, 2, 3, and 4 weeks) by 2 (CM vs. BSM) analysis of variance (ANOVA) which will yield effect sizes for time, and interactions of time by intervention. The primary dependent variables will be attendance at physician visits, saliva drug screen data (positive for buprenorphine and negative for illicit opioids), and prescription drug monitoring. We hypothesize that a greater number of CM participants will demonstrate adherence to buprenorphine-naloxone than BSM, but that those randomized to BSM will report increased time allocated to substance-free activities, decreased delayed reward discounting, and demand for opioid.

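### The Opioid Purchase Task announces the participant's chosen opioid but prices only pills and records neither drug nor unit, so a non-pill user's count cannot be read as demand for that opioid

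*Protocol*

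**What the plan says.** The instruction in Protocol 12.2.15 tells participants they will be asked "how many of your chosen opioids you would purchase depending upon how much they cost". The priced line then reads "How many opioid pills would you purchase if they were", and the answer column is headed "Number they would purchase". There are 17 prices: free, then $0.25 up to $20. No field records the drug, its form, its strength or the unit counted.

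Table 1 (Protocol 12.1) schedules the task at baseline and at the four sessions.

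The eligibility rule in Protocol section 7 is "Present for an appointment at CAS or ARC for buprenorphine-naloxone treatment of OUD". Neither it nor the screening questionnaire (12.2.3) restricts entry by form of opioid. The timeline followback (12.2.13) has separate rows for "Heroin on this day" and "Fentanyl on this day", apart from other non-prescribed opioids, and fentanyl is on the urine toxicology checklist.

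The SAP hypothesises that BSM participants will show "decreased delayed reward discounting, and demand for opioid". Demand is not among the primary dependent variables it lists. It names no demand index, unit or scoring rule.

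**The concern.** The two lines of the form name different commodities. A participant whose opioid is a pill can satisfy both. One who uses heroin or fentanyl has three options: state how many pills they would buy, answer 0, or count in some other unit that nobody writes down. The stored number does not show which they chose.

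This matters in two ways. A person who scores 0 at baseline because the product is not theirs has no room to show a fall. A person who counts differently at a later session shows a change in demand that is only a change of unit. Both distort the effect size for a named BSM hypothesis, in a pilot whose SAP is built around effect sizes. Once a count is stored without its unit, the unit cannot be reliably recovered.

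**Working it through.** The plan gives no power, SD or expected effect for opioid demand, so there is no stated figure to reproduce. The check is textual, followed by an illustration of size.

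**Does anything else in the documents supply the drug or unit?**

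- Opioid use disorder criteria (12.2.6) and treatment history (12.2.27): neither asks which opioid is used.
- Timeline followback and urine toxicology: these show which opioid classes were used, not which drug or unit the purchase answers refer to.
- SAP: no scoring or standardisation rule.

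Nothing fills the gap.

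**Size if non-pill users answer 0 throughout**

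Inputs: 20 per arm (Protocol 3.5: "We will randomize 20 participants to the CM group, and 20 participants to the BSM group"). The share h of non-pill users is assumed, because the documents do not give it; it could lie anywhere from 0% to 100%. Let δ be the true arm difference in mean change, σ the SD of change among pill users, and d = δ/σ. Assume the same h in both arms and a mean change near zero in the CM arm.

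- Observed mean difference: (1−h)δ.
- Average within-arm variance of change: (1−h)σ² + h(1−h)δ²/2. The constant-zero group adds no variance of its own, only the spread between the two groups.
- Required-sample multiple (variance ÷ squared difference, relative to h = 0): (1 + h·d²/2)/(1−h), which is about 1/(1−h) when d is small.
- Standardised effect relative to the true one, small d: √(1−h).

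| h (assumed) | Raw mean effect retained | Standardised effect retained (small d) | Sample multiple (small d) | Sample multiple at d = 0.5 |
|---|---|---|---|---|
| 25% | 0.75 | √0.75 = 0.87 | 1/0.75 = 1.33 | 1.03125/0.75 = 1.38 |
| 50% | 0.50 | √0.50 = 0.71 | 1/0.50 = 2.00 | 1.0625/0.50 = 2.13 |
| 75% | 0.25 | √0.25 = 0.50 | 1/0.25 = 4.00 | 1.09375/0.25 = 4.38 |

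At h = 50%, about 20 × 0.5 = 10 people per arm would carry information on change. If demand also falls in the CM arm, the between-group spread grows and the multiples rise somewhat.

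**Which summaries survive a difference in unit?**

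Let q(p) be the amount wanted at price p per pill-equivalent. Someone whose unit equals k pills reports Q(P) = q(P/k)/k at price P per unit.

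- Quantity when free: q(0)/k. It depends on k, but the ratio of follow-up to baseline does not if k is fixed.
- Breakpoint: k times the per-pill breakpoint. It depends on k.
- Expenditure: P·Q(P) = (P/k)·q(P/k). Its maximum does not depend on k, provided the price list reaches the peak.
- The list reaches only 20/k dollars per pill-equivalent, so it can stop too early for a costly unit.

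If k changes between sessions, only maximum expenditure is protected; the ratio is not.

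**The case against.** A reader might infer that heroin or fentanyl users cannot give a valid answer at all. The documents do not support that. The task is hypothetical, and such a participant can say how many pills they would buy. That is demand for a standard commodity, though not for the chosen opioid that the instruction announces.

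A reader might also infer a fourfold sample at h = 50%. That requires the SD to stay the same, but people who answer 0 throughout contribute no change variance, so the multiple is about two. Nor do the documents show the error favouring one arm; the demonstrable effect is attenuation and noise.

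Other points have weight:

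- The followback is a broad checklist and the urine panel belongs to the clinic, so listing heroin and fentanyl shows that their use is possible, not how common it is. An example of self-talk in 12.2.16 mentions pills.
- Session assessments are done with the interventionist (3.6.2), and each participant keeps one counselor (8.2.3). A consistent reading is therefore possible, and within-person change suffers less if it is kept. No script requires it.
- Table 1 cites a source for the task. Whether the pill wording comes from that source cannot be judged here, and rewording could cost comparability.
- No feasibility, satisfaction or adherence conclusion rests on this measure.

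These limit the size and importance of the point. They do not reconcile the two lines of the form or supply the missing unit.

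**Conclusion.** The point holds as an inexpensive improvement to an outcome outside the primary set. As written, the form gives counts whose commodity and unit are unknown for anyone whose main opioid is not a pill, so they cannot be read as demand for the chosen opioid or pooled as raw quantities across participants. The mismatch and the missing fields are established from the text.

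The size is conditional. It rests on an unknown h, on an assumed all-zero pattern and on similar h in both arms. With few non-pill users the effect is small. Participants whose opioid is a pill are affected only by the missing drug and strength.

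**What to change.** 1. Make both lines of 12.2.15 name the same commodity.
2. At baseline, record the participant's main non-prescribed opioid and its usual purchase unit. Print both in the priced question and reuse them unchanged at S1–S4. Specifying non-prescribed also settles whether prescribed buprenorphine counts.
3. In the SAP, define demand as within-person change on a scale that does not depend on the unit: proportional or log change (for example in quantity when free), or maximum expenditure in dollars. Do not pool raw quantity or breakpoint across units. State how zero values are handled, since a ratio or log is undefined there.
4. Add a sensitivity analysis in pill users.
5. Flag records already collected with the pill wording.

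The cost is one added field and a wording change, two form versions within N = 40, and some loss of comparability with the source instrument. Costlier units may be censored at the $20 top price; the number of participants still buying at $20 should be reported.

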12.2.16. Engagement in Substance Free Activities

Please rate the extent to which the following factors have been helpful in your recovery from opioids either currently or during periods in the past when you stopped using.

Check or mark the box to indicate your answer.

	1 Not at all helpful	2 Somewhat helpful	3 Very helpful
1) Change in your social group to avoid drug users		✓	
2) Increasing your social support, making new friends			
3) Developing a new hobby or reinvesting in previous hobbies (e.g., hunting, fishing, gardening)			
4) Exercising			
5) Running			
6) Reading			
7) Participating in yoga, meditation, or other forms of relaxation			
8) Spending more time with your family			
9) Change in your employment situation (working more or changing your job)			
10) Spending time in nature			
11) Addressing relationship or family issues/conflict			
12) Private religious activity (praying, meditating, reading scripture or religious books)			
13) Attending religious services			
14) Finding new ways to manage pain			
15) Taking medication for depression or anxiety			
16) Changing your diet to eat healthier foods			
17) Engaging more with social media (e.g., Facebook)			
18) Engaging less with social media (e.g., Facebook)			
19) Cooking/baking			
20) Changing your living situation/moving			
21) Drinking less alcohol or quitting drinking altogether			
22) Using less marijuana or quitting marijuana use altogether			
23) Quitting smoking			
24) Using more alcohol			
25) Using more marijuana			
26) Smoking more			
27) Engaging in creative activities (music, art, etc.)			
28) Getting involved with a team sport			
29) Getting involved in a community organization			
30) Volunteering			

31) Getting a pet			
32) Participating in a 12-step or other support group			
33) Seeing a professional counselor/therapist			
34) Helping others			
35) Taking a college class or educational/training program			
36) Sexual activity			
37) Eating more			
38) Addressing a health issue			
39) Avoiding high-risk situations for use/relapse			
40) Limiting access to money			
41) Telling your friends about your plan to stop using			
42) A change in your financial situation			
43) Reminding yourself about the risks of using			
44) Increasing your self-confidence/self-esteem			
45) Practicing positive self-talk (e.g., “I’m a good person” or “I can do this without pills”)			
46) Managing anger			
47) Other (write in)			

12.2.17. Time Spent on Activities Worksheet (to be uploaded as picture to database).

Instructions:

Please list how many hours EACH WEEK you spend doing each of the activities listed below.

For example, if you spend 2 hours each day playing video games, that would be 14 hours each week for the activity named “Watching TV or surfing the internet.”

	How many hours do you spend doing this activity EACH WEEK?
Family	
Work	

Education, hobbies, creative activities	
Exercise, time in nature, or self-care	
Watching TV or surfing the internet	
Religious or spiritual activity, community life	
Using opioids or other drugs/alcohol	
Substance recovery/treatment (includes counseling/medication visits and time in meetings like AA or NA)	
Socializing with people who are supportive of your recovery	
Socializing with people who are not supportive of your recovery	

12.2.18. Opioid Cravings Scale

	0	1	2	3	4	5	6	7	8	9	10
1. How much do you currently crave opiates?	Not at all										Extremely
2. In the past week, please rate how strong your desire to use opiates has been when something in the environment has reminded you of opiates	No desire										Extremely strong
3. Please imagine yourself in the environment in which you previously used opiates. If you were in this environment today and if it were the time of day that you typically used opiates, what is the likelihood that you would use opiates today?	Not at all										I'm sure I would use opiates

12.2.19. Buprenorphine-Naloxone dose log

How many days since your last visit to the Center for Addiction Science?	Enter #
How many days during this period did you skip your buprenorphine dose?	

12.2.20. Dosage of Buprenorphine-Naloxone Prescribed

(obtained from medical record at each session .)	
Medication name	
Mg prescribed (buprenorphine)	
MME calculation	

12.2.21. Treatment Satisfaction

The person who presented the material:						
1.	Was easy to talk to.	Strongly Disagree	Somewhat Disagree	Neutral	Somewhat Agree	Strongly Agree
2.	Was concerned about me.	Strongly Disagree	Somewhat Disagree	Neutral	Somewhat Agree	Strongly Agree
3.	Understands me.	Strongly Disagree	Somewhat Disagree	Neutral	Somewhat Agree	Strongly Agree
4.	Seemed competent and well trained.	Strongly Disagree	Somewhat Disagree	Neutral	Somewhat Agree	Strongly Agree
5.	Seemed well organized.	Strongly Disagree	Somewhat Disagree	Neutral	Somewhat Agree	Strongly Agree
6.	Gave me the opportunity to express my thoughts about treatment.	Strongly Disagree	Somewhat Disagree	Neutral	Somewhat Agree	Strongly Agree
7.	Helped me believe that I can change my opioid use if I want to.	Strongly Disagree	Somewhat Disagree	Neutral	Somewhat Agree	Strongly Agree
8.	Argued with me.	Strongly Disagree	Somewhat Disagree	Neutral	Somewhat Agree	Strongly Agree
9.	Tried to convince me that I needed to change my behavior.	Strongly Disagree	Somewhat Disagree	Neutral	Somewhat Agree	Strongly Agree
10.	Made me feel that it is up to me to make decisions about staying in treatment.	Strongly Disagree	Somewhat Disagree	Neutral	Somewhat Agree	Strongly Agree
11.	Gave me the chance to ask questions.	Strongly Disagree	Somewhat Disagree	Neutral	Somewhat Agree	Strongly Agree
The next questions are related to your treatment, not your counselor.						
12.	How interesting did you find this treatment?	Totally bad, boring	OK		Excellent, it was great	
13.	How personally relevant did you find this treatment?	Not at all relevant to me	OK		Excellent, it was very relevant to me	
14.	How effective do you think this treatment was in helping you stay in treatment?	Not at all effective	Somewhat effective		Very Effective	

15.	Those who drop out of treatment only: Please indicate how likely you are to restart buprenorphine treatment in the near future	I will not change my smoking	Unsure		I will change my smoking	N/A, already quit
16.	How effective, overall, do you think this program will be in helping people stay in opioid treatment?		1 = Not useful or effective 10 = Highly effective. The best treatment I could imagine.			
17.	What components of the treatment were most effective for you?		(Open ended)			
18.	Can you think of any ways to make this intervention more effective and user-friendly?		(Open ended)			
19.	What initially made you want to enroll in the study?	a.	b. I wanted help staying in treatment c. Gift cards d. One-on-one counseling e. Other (specify)			
20.	What was your motivation to stay in the study and complete your sessions?		(Open ended)			

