3.2. Objectives

Our goal with this research is to examine the feasibility, satisfaction rates, and efficacy of two interventions, Contingency Management (CM) and Brief Motivational Intervention + Substance Free Activities + Mindfulness-Based Adherence Promotion (BSM), to improve buprenorphine-naloxone adherence during the treatment initiation phase (first 5 physician visits). Once feasibility, satisfaction, and efficacy are acquired, Project 4 (the randomized clinical trial associated with the R33 award phase) will be conducted.

Feasibility in this trial is defined as the ability to recruit, treat, and follow up participants within the target timeline and costs. Recruitment, intervention, and retention actuals (vs. goals) will be evaluated by investigators and the Data Safety Monitoring Board (DSMB) which will be convened every 6 months.

Satisfaction will be measured with a measure developed from previous research.

Efficacy will be evaluated in terms of participant adherence to buprenorphine-naloxone treatment: Showing up to scheduled appointments with their physician at the Center for Addiction Science AND the presence of buprenorphine in the participant's urine screen, conducted as a part of buprenorphine treatment.

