3.3. Design and Outcomes

This project will use a randomized design to compare treatment satisfaction and effectiveness of Contingency Management (CM) and Brief Motivational Intervention + Substance Free Activities Session + Mindfulness-Based Adherence Promotion (BSM) for medication adherence in patients who are initiating buprenorphine-naloxone treatment at our Center for Addiction Science (N=40). The interventions will take place across the first 4 physician visits of buprenorphine-naloxone treatment, starting after treatment intake.

Primary outcomes will include feasibility and satisfaction at the fourth weekly intervention visit, and an efficacy comparison of intervention group differences in buprenorphine-naloxone treatment adherence, defined as (1) attendance at physician visit AND (2) buprenorphine-naloxone presence in urine toxicology.

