3.4.3. Final Assessment (Participant)

All participants will complete a blinded treatment satisfaction follow-up assessment shortly after completing Session 4 Part 1. Session 4 Part 2 assessment is to be conducted by an assessor blind to study conditions.

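### Satisfaction item 15 asks drop-outs about restarting buprenorphine but offers answers about smoking, so as printed it cannot measure that likelihood

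*Protocol*

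**What the plan says.** Protocol 12.2.21 lists 20 satisfaction items. The stem of item 15 is: "Those who drop out of treatment only: Please indicate how likely you are to restart buprenorphine treatment in the near future". Its response row gives "I will not change my smoking" at the low end, *Unsure* in the middle, "I will change my smoking" at the high end, and "N/A, already quit" as an opt-out.

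The standing of the instrument is set in three places. Protocol 3.3 states: "Primary outcomes will include feasibility and satisfaction at the fourth weekly intervention visit". Protocol 3.2 gives its origin: "Satisfaction will be measured with a measure developed from previous research". Protocol 3.4.3 gives its timing: "All participants will complete a blinded treatment satisfaction follow-up assessment shortly after completing Session 4 Part 1". Protocol 3.6.3 and Section 14 place it in a follow-up call made by a research assistant blinded to arm.

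The SAP names satisfaction as a focus of the analysis but does not say how the measure is scored. The Protocol does not say either, and neither document says how item 15 is to be used.

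**The concern.** The question concerns one behaviour and both end anchors concern another. A drop-out who is certain to restart buprenorphine has no option that says so, and neither does one who is certain not to. The research assistant on the call must either read out options that make no sense or improvise. The manual gives no instruction for that, although its Preface says it exists to keep data collection consistent.

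What is at stake is one piece of information on a group the study wants to understand. Protocol 8.2.1 and 8.6 keep drop-outs under assessment to learn why they left and whether they seek treatment elsewhere. Whether they intend to come back belongs with those questions. The pilot also precedes Project 4 (Protocol 3.2), so an uncorrected form could be carried forward.

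**Working it through.** No arithmetic applies, and the plan states no figure to reproduce. The check sets the stem against each answer and then looks for anything elsewhere that would rescue the item.

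1. **Stem against options.**
   - Low anchor: about changing smoking. It does not answer the stem.
   - *Unsure*: neutral. It fits the stem at face value.
   - High anchor: about changing smoking. It does not answer the stem.
   - Opt-out: "N/A, already quit". For a person who has left treatment this could mean having quit smoking, opioids or the treatment itself. It does not identify someone who has already restarted.

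   One usable midpoint with no valid end on either side cannot order respondents by likelihood.

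2. **Is it damage from reading the PDF?** No. The smoking labels are complete and grammatical and sit in the item 15 row. Items 12 to 14 and item 16 carry anchors that match their own questions. A second leftover appears in the Participant Withdrawal section (numbered 18.13.3), where interventionists are told to mention smoking cessation. Both are consistent with text carried over from a smoking study, with the item 15 stem adapted and its answers left behind.

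3. **Does another item supply the information?** No. Section 12.2.29 asks those who stopped treatment whether they are receiving buprenorphine-naloxone, or any treatment for opioid use disorder, at present. Treatment history (12.2.27) looks backwards. Satisfaction item 14 asks whether the intervention helped the person stay in treatment. None asks about the intention to restart.

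4. **Does a scoring rule bring item 15 into the primary outcome?** None is given. The instrument mixes 11 agreement items (1 to 11), three anchored ratings of the intervention (12 to 14), item 15, a 1-to-10 rating (16), three open-ended questions (17, 18, 20) and a categorical question on reasons for enrolling (19). The count is 11 + 3 + 1 + 1 + 3 + 1 = 20. No single total is evident.

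5. **Extent.** One item of 20 is affected and 20 − 1 = 19 are not. Only drop-outs who complete the Session 4 call are asked item 15. The planned sample is about 40 (Protocol 3.5), and the documents give no expected number of drop-outs.

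**The case against.** The strongest reply is that this is a wording slip with little consequence. Item 15 asks about intention and is not on its face a satisfaction rating. The manual may not match the form in use either: responses are entered in FileMaker, which cannot be seen from these documents, and an interviewer may have recorded answers by the evident meaning of the stem. All of that is fair, and it limits what can be claimed. It does not remove the defect, because the manual describes itself as the official reference for conduct and its text for this item is wrong.

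Three stronger readings are tempting, and the documents do not support them.

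- **That the satisfaction outcome is corrupted, perhaps unequally by arm.** This needs a score that includes item 15, and neither document defines one.
- **That a large share of the sample is affected.** A reader might assume 30% to 50% drop-out and reach 0.3 × 40 = 12 to 0.5 × 40 = 20 participants. The documents give no such rate, and the sum counts every drop-out as a respondent. Completion of the call by drop-outs is itself uncertain. Section 14 ties the Session 4 gift card to completing the intervention as well as both assessment parts, whereas Protocol 8.6 says drop-outs no longer receive the intervention but still earn the card for the assessment.
- **That the item yields nothing and every answer must be thrown away.** *Unsure* does fit the question, and whether any answers were taken with the printed anchors is unknown.

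**Conclusion.** The point stands as a minor one: item 15 is wrong as written. With both end anchors on a different behaviour, it cannot measure the likelihood of restarting buprenorphine, and the manual has no substitute for it. The damage is confined to that item and to the drop-outs who answer it. The rest of the satisfaction measure, and the adherence outcome, are untouched.

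The conclusion rests on the printed text alone and needs no assumed drop-out rate. Two matters remain open: whether the live form carries the same wording, and whether the team intended item 15 to count towards any total.

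**What to change.** - Replace the item 15 options, in both the manual and the live form, with anchors on the likelihood of restarting buprenorphine treatment (for example *Not at all likely*, *Unsure*, *Very likely*) and a matching not-applicable option (for example *already restarted*). Other label sets would serve as well, provided they answer the stem.
- State in the SAP that item 15 is reported separately, for drop-outs only, and stays outside any satisfaction total.
- Check which wording was read out or programmed for participants already assessed. Report answers taken with the smoking anchors as not interpretable. Answers taken with correct wording can stand.

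The cost is one line on the form, one sentence in the SAP and a check of the database. The downside is that some or all earlier item 15 answers may be lost.
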